6.7 Sample Size Determination- Parent (Main) Study

For **Aim 1** we hypothesize that BAS+ vs. SC will have higher smoking abstinence rates and less PCWG at the 26-week follow-up (primary outcomes). Power calculations were all approximated as t-tests or z-tests, and conducted using PASS Software (Power and Sample Size, NCSS Software, Kaysville, UT), Bonferroni corrected for two primary outcomes ($p=.025$). Proportions of abstinent and smoking subjects will be compared using the log of the odds-ratio, which has a known variance. Informed by smoking cessation counseling plus TN research, we anticipate that the 6-month abstinence rate will be 13% in the SC (control) group and 25% in the BAS+ group (consistent with a persistent effect of BAS+ after the discontinuation of TN). A sample of 213 per group provides 82% power to detect this 12% difference in quit rates at 6 months. This represents a clinically meaningful effect and corresponds to a small effect size ($\delta=.15$). For PCWG, we will include all participants in the analysis, while testing a smoking status x treatment interaction. Informed by epidemiological and clinical studies of PCWG, we will have 80% power to detect a 6 pound (2.72 kg) difference in PCWG between BAS+ and SC, using the interaction term. We expect BAS+ vs. SC will have less post-cessation food intake (secondary outcome) at the 26-week follow-up. We have 80% power to detect a 320 kcal/day difference between the two groups ($p = .05$). In light of these considerations (i.e., 213 subjects per arm; total 426) and an attrition estimate of 15% across accrual, we will recruit a total of 245 subjects to each arm for a total of 490 subjects (~500).

For **Aim 2**, we hypothesize that BAS+ vs. SC, will increase alternative reinforcers, and reduce food reward, the RRVF, and food cue-induced craving. These changes, in turn, will predict less food intake and PCWG, and greater smoking abstinence at the 26-week follow-up. Using structural equation modeling, we will test the treatment effect on the slope of the mediators versus time, with pre-quit values representing the intercepts. We will examine the proportion of

CONFIDENTIAL

This material is the property of the University of Pennsylvania. Do not disclose or use except as authorized in writing by the study sponsor

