treatment effect explained, and test with a delta method generated z-score (Type I error of .05). There are four proposed mediating pathways between treatment and outcome, so our Type I error will be corrected to 0.0125. For smoking abstinence, a sample of 426 gives us 80% power to detect small effects ($\delta=0.32$) for changes in the proposed mediators, where serial observations are uncorrelated within subject. This also applies to individual path strength. Even a modest within-subject correlation ($\rho=0.3$) provides 80% power to detect a small treatment effect ($\delta=0.20$). For PCWG, smoking status will be treated as a time-varying covariate, where changes in weight are represented as a slope factor (based on observed repeated measures of weight). With a sample of 426, we will have power to detect a small effect ($\delta < 0.20$), even without adjustment for within-subject correlation.

As an **exploratory aim**, we will test whether females, or participants with greater pre-treatment depression symptoms, or weight concerns, are more likely to experience PCWG and more likely to benefit from BAS+ vs. SC. We will test an interaction effect predicting that the effects of the BAS+ will be more pronounced for females, and for those who have greater depression symptoms, or weight concerns. For smoking abstinence, with a 6-month quit rate difference of 12% (25% BAS+ vs. 13% SC), we approximated power by simulation using a z-test based on the ratio of odds ratio (ORR). If this effect, for example, is completely derived from a larger effect of BAS+ among females (no effect in males), then we will have 80% power to detect an interaction with 213 subjects per treatment arm. This corresponds to an odds ratio of ~4.0 for a BAS+ effect in females and an odds ratio of 1.0 in males. All tests will be performed at a $p < .05$ significance level. We approximated the same interaction for PCWG using the z-score. Restricting the sample to abstinent participants (54 BAS+, 28 SC) with continuous moderators dichotomized at the median, a standard deviation of 3.5 kg, and a standard error of 1.63 for the interaction, we will have 80% power to detect an interaction difference of 4.7 kg (10.4 lbs.).

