Aim 2 will involve assessing the direct effect of treatment on smoking cessation and PCWG, and the indirect or mediated effects of treatment on these outcomes through the hypothesized sequential mediating mechanisms using structural equation modeling. Mediation exists when a relationship between treatment and smoking cessation or PCWG is accounted for in full, or in part, by one or a set of intervening variables (e.g., alternative reinforcers, food cue-induced craving, food reward, RRVF). Longitudinal change in the mediators will be represented with a slope factor (based on observed repeated measures of each mediator). We will assess the mediation strength (absent to complete) by estimating the effect proportion mediated ($\beta_{\text{indirect}}/\beta_{\text{total}}$), and determine the significance of effects with Delta method standard errors, with bootstrapped standard errors for validation. We will employ a weighted least squares estimation technique with robust standard errors, and a mean and variance adjusted chi-square test for the estimation of model parameters. Multiple indicators of model performance will be used, including the χ^2 test, Comparative Fit Index ($< .95$), Weighted ($<.90$) and Standardized Root Mean Square Residual ($<.80$), Root Mean Squared Error of Approximation ($< .05$), and an examination of standardized model residuals. Bayesian Information Criterion and Scaled Unit Information Prior BIC will be used to compare different models.

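### Parent Aim 2 tests mediation with a symmetric delta-method z, which has about 29% power when both paths are at the strength for which 6.7 states 80%; a percentile bootstrap interval has about 62%

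*Combined protocol and SAP*

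**What the plan says.** Section 6.10, Aim 2, fits a structural equation model with slope-factor mediators. "We will assess the mediation strength (absent to complete) by estimating the effect proportion mediated", that is, indirect over total effect. It will then "determine the significance of effects with Delta method standard errors, with bootstrapped standard errors for validation".

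Section 6.7 describes the same test as applied to the proportion of "treatment effect explained, and test with a delta method generated z-score (Type I error of .05"). It then adjusts alpha: "There are four proposed mediating pathways between treatment and outcome, so our Type I error will be corrected to 0.0125".

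On power, 6.7 states: "For smoking abstinence, a sample of 426 gives us 80% power to detect small effects ($\delta=0.32$) for changes in the proposed mediators", in the case "where serial observations are uncorrelated within subject". It adds: "This also applies to individual path strength". The sample is "213 subjects per arm; total 426". No power is given for an indirect effect or for the proportion mediated. No bootstrap confidence interval, percentile or bias-corrected, is named for parent Aim 2.

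**The concern.** An indirect effect is the product of two paths: treatment to mediator (a) and mediator to outcome (b). Unless at least one path is strong, the estimated product is skewed, and a z that assumes symmetry rejects too rarely. Replacing the delta-method standard error with a bootstrapped one changes the estimate of spread but keeps the symmetric test, so the planned validation would tend to agree with the weak test. A percentile interval follows the skew. Dividing by an imprecise total effect weakens the z further.

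Aim 2 is meant to show how BAS+ works. If the test misses real mediation at the path sizes for which the study was planned, a non-significant result may be read as absence of mediation.

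**Working it through.** **Inputs.** From 6.7: 213 per arm, alpha 0.0125 (0.05/4), delta 0.32, no within-subject correlation, and the same strength for individual paths. From 4.2: a current target of about 340, or 170 per arm. Assumed, because the documents do not say: two-sided tests, a continuous outcome, a single mediator, and a b path with the same expected z as the a path.

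**The plan's own figure.** The two-sided critical value at 0.0125 is 2.498. The delta with 80% power is (2.498 + 0.842) × √(4/426) = 0.324, which matches 0.32. At exactly 0.32 the expected z is 0.32 × √(213/2) = 3.30, with power 78.9%. The 80% therefore reproduces, as the power of one path.

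**Indirect effect, both paths at that strength.** The delta-method statistic is z_a × z_b / √(z_a² + z_b²). With both at 3.30 it centres near 3.30/√2 = 2.34, below 2.498, so power should be under 50%. The figures below come from draws of (z_a, z_b) and from simulated trials with 2,000 bootstrap resamples each. Small differences between runs are simulation error.

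| Test, both paths at delta 0.32, alpha 0.0125 | N = 426 | N = 340 |
|---|---|---|
| Delta-method z | 29–30% | 14–16% |
| z on bootstrapped standard errors | 28–29% | 15% |
| Percentile bootstrap interval | 61–62% | 42–45% |
| Joint significance of both paths | 61–62% | 45–46% |

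At N = 340 the expected z per path falls to 0.32 × √(170/2) = 2.95.

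**Type I error, one path null and the other at 3.30.** The delta-method z rejects about 0.1–0.2% of the time. The percentile interval rejects roughly 0.8–1.35%, against a nominal 1.25%. The extra power is therefore not bought with excess false positives.

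**Stronger paths.** Section 6.7 also states 80% power at delta 0.20 if the within-subject correlation is 0.3. A true delta of 0.32 in that setting has an expected z of about 3.34 × 0.32/0.20 = 5.3. With one path at 5.3 and the other at 3.30, the delta-method z has about 65% and joint significance 79%. With both at 5.3 the figures are 98% and 99%.

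**Uncorrected alpha 0.05, N = 426, both paths at delta 0.32.** Delta-method z 67%, z on bootstrapped standard errors 64%, percentile interval 81%.

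**Proportion mediated.** With a direct effect of 0.25 SD, which is an assumption, the delta-method z on the ratio has about 6% power at N = 426 and alpha 0.0125. The documents give no direct effect, so this shows direction only.

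**The case against.** The strongest reply is that two paths both at the detection limit is the least favourable case in 6.7. The 0.32 holds only without within-subject correlation, and with stronger paths the loss shrinks and nearly vanishes. That stands. A reader might infer that the test has half the available power in general, or that true mediation would usually be missed. The documents do not support either reading, because 6.7 does not quantify the b path separately and allows for stronger a paths.

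The simulation is also simpler than the plan. The 0.32 is introduced for abstinence, a binary outcome, while for weight gain 6.7 quotes an effect below 0.20. Slope-factor mediators, sequential chains and weighted least squares were not simulated. This limits the precision of the percentages. It does not remove the skewness of a product of estimates.

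The delta-method z errs on the safe side, so it invites no false claims of mediation, and Aim 2 is not the primary aim. Both points are fair. They argue for keeping the delta-method result as a sensitivity analysis. They do not argue for keeping it as the deciding test.

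Two other readings are tempting. One is that the plan already has the better bootstrap and need only promote it. It does not: 6.10 names bootstrapped standard errors, which give no gain. The other is that 6.7 presents 80% as power for mediation. It ties the figure to changes in the mediators and to individual paths. What is missing is a statement for the indirect effect.

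**Conclusion.** The concern holds in a limited form. Parent Aim 2 rests on a symmetric z, and its planned check has the same weakness. At the path strength for which 6.7 states 80%, power for the indirect effect is about 29%, against about 62% for a percentile bootstrap interval whose type I error is near nominal. This assumes N = 426, two-sided alpha 0.0125, equal a and b paths, uncorrelated serial observations, a continuous outcome and one mediator. The shortfall is smaller if either path is stronger. It is larger for the z on the proportion mediated, by an amount that the documents do not allow one to fix. At the target of about 340 in 4.2, both tests lose power, to about 15% and 45%.

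**What to change.** In 6.10 and 6.7, make the 98.75% percentile bootstrap confidence interval for each indirect effect the test of mediation, in place of the delta-method z and the bootstrapped standard errors. Keep the delta-method result as a sensitivity analysis. Report the proportion mediated with its bootstrap interval, as descriptive only.

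In 6.7, say that the 80% is for a single path. Add the power for an indirect effect, with its assumptions, at the sample size actually targeted: about 62% at N = 426 and about 45% at N = 340 when both paths are at delta 0.32. One fixed figure would not serve both sample sizes.

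The cost is SAP wording, computing time and a less favourable Aim 2 power statement. No new data or participants are needed.

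### Two of the four numeric fit criteria for the Aim 2 mediation models are wrong as printed: the CFI inequality is reversed, and an SRMR limit of .80 screens out almost nothing

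*Combined protocol and SAP*

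**What the plan says.** The Aim 2 paragraph of Section 6.10 (Statistical Methods, parent study) describes the mediation models. Each mediator's change over time is a slope factor, and estimation is by robust weighted least squares: "We will employ a weighted least squares estimation technique with robust standard errors". On fit, it says "Multiple indicators of model performance will be used". It then names the chi-square test, "Comparative Fit Index ($< .95$), Weighted ($<.90$) and Standardized Root Mean Square Residual ($<.80", then "Root Mean Squared Error of Approximation ($< .05", and finally "an examination of standardized model residuals". Two versions of BIC are reserved for comparing models.

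No rule says how the indices combine or what follows if one is missed. No other section restates or corrects the values. Section 6.7 gives the sample size for these models: "a sample of 426 gives us 80% power to detect small effects".

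**The concern.** All four bracketed limits use the less-than sign. For WRMR, SRMR and RMSEA a smaller value means better fit, so the sign marks acceptable fit. CFI runs the other way, and the same sign there makes poor fit the criterion. Separately, SRMR is an average residual correlation, and .80 is so large that a model with no associations at all will usually meet it.

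Aim 2 is one of the parent study's two numbered aims, and its proportion-mediated estimates can be read only if the model fits adequately. With two of four numeric criteria unusable, the analyst must either follow a criterion that turns good models away or depart from the written plan. A departure made after the data are in hand would look post hoc.

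**Working it through.** **Plan's own figures.** The cut-offs are chosen, not calculated, so there is nothing to reproduce. The one computed figure nearby is the Aim 2 alpha in Section 6.7: 0.05/4 = 0.0125, which reproduces and is not affected.

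**CFI, by definition.** With M the fitted model and B the independence (baseline) model,

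CFI = 1 − max(χ²_M − df_M, 0) / max(χ²_B − df_B, χ²_M − df_M, 0).

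- Perfect fit: χ²_M does not exceed df_M, the numerator is 0 and CFI = 1. Since 1 is not below .95, the model fails the printed criterion.
- Independence model: M = B, the ratio is 1 and CFI = 0. Since 0 is below .95, the model meets it.

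**SRMR of a null model.** Let p variables share a common correlation r, and fit a model with free variances and no associations. The p(p − 1)/2 off-diagonal residuals all equal r, and the p diagonal residuals are 0. Averaging squares over p(p + 1)/2 elements gives

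SRMR = r × sqrt((p − 1)/(p + 1)).

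If the correlations differ, r is replaced by their root mean square. Section 6.5.4 gives four waves for the laboratory tasks (weeks −2, 1, 4, 8) and five for the alternative-reinforcer scale (adds week 2). The values 8 and 20 stand for larger joint models.

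| p | sqrt((p − 1)/(p + 1)) | r needed for SRMR above .80 | r needed for SRMR above .08 |
|---|---|---|---|
| 4 | .775 | impossible (1.03) | .103 |
| 5 | .816 | .98 | .098 |
| 8 | .882 | .91 | .091 |
| 20 | .951 | .84 | .084 |

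If the diagonal is left out of the average, SRMR is simply r, and the null model still meets the limit unless r reaches .80. None of this depends on sample size.

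**Illustration of the indices together.** The simulation used N = 426 (Section 6.7), four waves at weeks −2, 1, 4 and 8, and 200 data sets per model from one linear growth population. The population values are assumptions, not from the documents: time scaled 0 to 1, mean slope 0.6, intercept variance 0.5, slope variance 0.4, covariance 0.05, residual variance 0.5. Maximum likelihood stood in for weighted least squares. WRMR, the chi-square test and the residual check were not simulated.

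| Result | Correct growth model | Misspecified no-slope model |
|---|---|---|
| Mean CFI | .998 | .73 |
| Mean SRMR | .022 | .106 |
| Mean RMSEA | .013 | .21 |
| CFI < .95 (as printed) | 0% | 100% |
| SRMR < .80 (as printed) | 100% | 100% |
| SRMR < .08 | 100% | 13% |
| RMSEA < .05 (as printed) | 94% | 0% |
| CFI, SRMR and RMSEA all as printed | 0% | 0% |
| CFI ≥ .95, SRMR < .08, RMSEA < .05 | 94% | 0% |

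Taken alone, the printed CFI criterion sorts the two models the wrong way round, and the printed SRMR limit does not separate them. Taken jointly with RMSEA, the wrong model is still refused, but so is the right one.

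**The case against.** A reader might infer that badly fitting mediation models will pass, or that the plan will select them. The documents do not support that. RMSEA and WRMR carry limits in the right direction, the chi-square test and residuals are also examined, and no pass/fail rule lets CFI or SRMR decide alone. In the illustration RMSEA rejected the misspecified model in every run. Nor does Section 6.10 make the mediation conclusions conditional on these cut-offs: models are compared by BIC, and mediation is judged by the proportion mediated and delta-method standard errors checked by bootstrap. All of this stands, and it limits the consequence to what each index does by itself.

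The values also look like slips, and a sensible analyst would be unlikely to discard a model with CFI = 1.00. That is probably so, but the printed line is the pre-specified one. For CFI, a symbol misread from the PDF cannot be excluded, although a greater-than sign survives in the voxelwise threshold of Section 6.11. A misread sign would not explain .80.

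Could the brackets instead mark values that signal poor fit? Then CFI would be right, but RMSEA, WRMR and SRMR would all be reversed. No single reading of the sign makes the list consistent.

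Finally, calling the SRMR limit ten times too loose is tempting but relies on .08, which the documents do not state. That .80 is too loose follows from the algebra alone.

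**Conclusion.** The point holds index by index. The printed CFI criterion is reversed: it fails a perfect model and admits the independence model. The printed SRMR limit cannot reject a null model on 4 variables, and with 5, 8 or 20 it does so only above common correlations of about .98, .91 and .84. The clearer practical harm, if the CFI line is followed literally, is that well-fitting models are turned away. The claim that misfitting models would get through the whole set of checks is not established.

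The CFI result rests on the definition of the index. The SRMR result rests on the null-model formula with a common (or root mean square) correlation. The simulation is illustrative only. The issue is confined to checking model fit in Aim 2. It does not touch the primary outcomes, the 0.025 or 0.0125 alpha levels, or the sample size.

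**What to change.** In the Aim 2 paragraph of Section 6.10, change the CFI criterion to greater than .95 and the SRMR criterion to less than .08. Leave the WRMR and RMSEA limits as they are. The .08 is the customary value, offered as an assumption; with it, a null model is rejected once the common correlation exceeds about .10 (.084 to .103 for 20 down to 4 variables). If the source PDF already shows a greater-than sign for CFI, only the SRMR value needs changing.

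The cost is one line of text, with no change to data collection, sample size or the primary analysis. It should be made before the mediation models are fitted. A further sentence on how the indices will be weighed together would help, but this correction does not depend on it.

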6.11 Statistical Methods - Neuroimaging Sub-Study

fMRI preprocessing will use standard algorithms in FSL (FMRIB's Software Library, www.fmrib.ox.ac.uk/fsl) including distortion correction, slice-time correction, motion correction, spatial smoothing, high-pass filtering (120s) and co-registration to the structural MRI. Quality assessment (QA) procedures will examine global and ROI based temporal signal-to-noise ratio (tSNR), absolute and relative motion, and signal spike count. Following preprocessing, subject-level BOLD timeseries analysis is carried out using the general linear model (GLM) as implemented in FSL, with a canonical double-gamma hemodynamic response function (HRF) for convolution, and linear contrasts to estimate task-specific BOLD responses for each individual session. To enhance sensitivity and reliability, including motion regressors in the model will reduce potential motion artifact. For group-level Image analysis, Subject-level statistical maps will be transformed into a common anatomic space (Montreal Neurological Institute, MNI) for group-level analysis. A priori region of interest (ROI) analyses will focus on specific regions for each task. For the n-back, primary ROIs will be MF/CG, and bilateral DLPFC. For the cue and reinforcement tasks, primary ROIs will be VS and ventromedial PFC; secondary ROIs will include MF/CG, amygdala, OFC, and insula. Percent signal change and activation extent within these ROIs will be used for statistical tests of key hypotheses. In addition, we will use voxel-wise random effects analysis in FSL to test for the effects outside of predicted regions. These voxelwise analyses will be conservatively corrected using $Z>3.09$ and cluster probability (family-wise error) $p<0.001$.

Hypothesis Testing. Percent signal change data will be exported for hypothesis testing using Stata (StataCorp, Texas).

CONFIDENTIAL

This material is the property of the University of Pennsylvania. Do not disclose or use except as authorized in writing by the study sponsor

Aim 1: Identify effects of BAS+ (vs SC) treatment on food related neural activity and behavior: These comparisons are all between subject, and will be analyzed using mixed models regression (xtmixed, StataCorp, Texas). The model predictors will include a binary indicator for group (BAS+ vs. SC). The hypothesis will be tested using the z-score corresponding to the main effect of group. Covariates can be included in the model to control error (sex, BMI, nicotine dependence, age, weight concerns), although we do not expect to make large gains for adding subject-level controlling variables in a mixed model.

Aim 2: Evaluate the relative contribution of these neural processes to post-cessation caloric intake: Our outcome variable is average daily calories based on food recalls. The first comparison (pre vs. post-treatment) is within-subject, and will be analyzed using mixed models regression with subject specific random effects. As before, we include a binary predictor for condition, a categorical indicator for serial day, and we will test using the z-score corresponding to condition. For testing candidate mediators, we will again model calories using mixed models, entering variables as time-varying (condition varying) predictors, along with subject specific random effects. Finally, we will build the larger model, looking for confounding that represents potential mediation. For this purpose, we will use regression-based multi-equation path models. Path Analysis partitions a directly measured bivariate relationship, for example, between abstinence and calories ingested, into direct and indirect causal paths, to tease apart the important components mediating the response. We will deem that mediation has occurred when a relationship between abstinence and food intake accounted in full, or in part, by one or more of the intervening variables (BOLD signal change or subjective responses in cessation vs. smoking). We will assess the strength of the indirect effects through confidence intervals, evaluate the proportion mediated (i.e., partial or complete mediation), and determine significance with Delta method standard errors. To assess the level of mediation for a pathway, we will estimate the ratio of the indirect effect to the total effect (i.e., effect proportion mediated $\beta_{\text{indirect}}/\beta_{\text{total}}$).

Aim 3: Test whether cessation-induced working memory deficits moderate the relationship between neural responses to food cues and reinforcement and food intake: This implies a 3-way interaction for a repeated measures analysis (e.g. cessation condition by food reinforcement by working memory on food intake). We will reduce the complexity and eliminate the repeated measures by conducting the analysis using difference scores (pre vs post), and will use multiple linear regression to analyze the differences in food intake. We will model the brain responses to cue reactivity and to food reinforcement separately. The models will contain a term for the difference in BOLD signal, and we will introduce a candidate moderator.

